4.2.2. Dosing Rationale

As this study is the first-in-human (FIH) study, the initial dose of SKL24741 has been conservatively selected according to the United States Food and Drug Administration (FDA) guidance document entitled “Estimating the Maximum Safe Starting Dose in Initial Clinical Trials for Therapeutics in Adult Healthy Volunteers” (FDA Guidance for Industry, 2005).

The dose levels planned for the Phase 1 clinical trial are based on the overall safety and tolerability profile of SKL24741 established in the nonclinical program. In the GLP 28-day oral toxicity studies, the FDA-recommended no observed adverse effect level (NOAEL) doses of 15 mg/kg/day for rats and 10 mg/kg/day for dogs were used for the human starting dose calculations. Based on the results of the SKL24741 toxicology studies, rats were

considered the most sensitive species. On a body surface area (BSA) basis, human equivalent dose (HED) in rats is $15 \text{ mg/kg/day} \div 6.2 = 2.42 \text{ mg/kg/day}$; HED based on the NOAEL in dogs is $10 \text{ mg/kg/day} \div 1.8 = 5.56 \text{ mg/kg/day}$. By applying a 10-fold safety factor to the HED of 2.42 mg/kg/day for rat NOAEL, the maximum recommended starting dose (MRSD) for a Phase 1 clinical study in healthy volunteer is 0.242 mg/kg (or 14.5 mg based on an assumed human weight of 60 kg [calculation = $2.42 \text{ mg/kg/day} \div 10 \text{ (safety factor)} \times 60 \text{ kg}$]).

Table 3 provides an overview of the NOAELs from the 28-day GLP repeated-dose toxicology studies and the systemic exposures at the NOAEL dose levels. The HED, MRSD, and calculated human starting dose are also presented.

Table 3: Summary of NOAELs, systemic exposure at the NOAEL dose levels, MRSD and human starting dose

Study No. / Species	NOAEL (mg/kg/day)	AUC at NOAEL Day 28 (µg*hr/mL)	C _{max} at NOAEL Day 28 (µg/mL)	Scaling Factor	HED (mg/kg)	MRSD (10X Safety Margin = HED÷10) (mg) (60-kg human weight)
22T0022 / Rat	15*	61.2	3.32	6.2	2.42	14.5
22T0023 / Dog	10*	21.7	2.61	1.8	5.56	33.3

AUC = area under the concentration-time curve; C_{max} = maximum concentration; HED = human equivalent doses; MRSD = maximum recommended starting dose; NOAEL = no observed adverse effect level.

*NOAELs based on FDA recommendation

Based on these data from the most sensitive species (rat), the MRSD is approximately 14.5 mg with a 10-fold safety factor applied to the HED (HED ÷ 10). However, a larger safety factor of approximately 15 was applied to the HED (HED ÷ 15) due to steep dose-toxicity profile in rats and dogs (Section 4.1.1). Therefore, the starting dose of this FIH clinical study will be a single oral dose of 10 mg of SKL24741. With this starting dose, a safety factor would be approximately 33 from the HED derived from the dog.

The first cohort of the single ascending dose (SAD) study will receive a single dose at the Dose 1 level (i.e., 10 mg) and subsequent cohorts will receive doses up to 1000 mg (as a single dose) based on the prediction from allometric scaling and in silico assessment.

However, dose levels of SKL24741 will be adjusted if needed based on plasma exposure, safety and tolerability observed at each dose level during the study.

The single-dose escalation scheme (Part A) is designed to explore a range of doses up to the plasma exposure observed at the NOAEL of 10 mg/kg/day in dogs (Day 28 mean combined sex C_{max} and AUC values of 2.61 µg/mL and 21.7 µg*hr/mL, respectively; **Table 3**) if the safety and tolerability allow reaching this plasma exposure. A few additional single dose levels beyond the dog NOAEL exposures may be considered if the safety and tolerability warrant a higher dose of SKL24741. However, the dose escalation increment will not exceed 1.5-fold between each dose level due to the steep dose response observed in toxicology species (Section 4.1.1). The institutional review board (IRB) will be notified prior to initiating these additional cohorts. In any case, the plasma exposure in humans will not

exceed the exposure observed at the NOAEL of 15 mg/kg/day in rats (Day 28 mean combined sex C_{max} and AUC values of 3.32 $\mu\text{g}/\text{mL}$ and 61.2 $\mu\text{g}^*\text{hr}/\text{mL}$, respectively).

After the first dose level, if drug exposure in humans differ from what is expected from nonclinical studies, the dose-escalation scheme may be re-evaluated. The dose level selected to assess the preliminary food and gender effects may also be re-evaluated. Any changes to the dose escalation scheme will be reviewed and approved by the Sponsor and submitted to the IRB.

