4.2.1. Study Design Rationale

A schematic of the proposed study design is presented below in [Figure 1](#).

The study includes a sequential cohort design that is intended to optimize subject safety and assess tolerability, safety, and PK of SKL24741. In the single-dose escalation part of the study (Part A), tolerability, safety, and PK of SKL24741 will be assessed in healthy male subjects under fasting condition. At an appropriate dose based on PK results, one dose

cohort will be repeated with the subjects under fed condition, in order to evaluate the magnitude of the food effect on the disposition of SKL24741. To assess the gender effect on the disposition of SKL24741, female subjects will be treated at one dose level under fasting condition.

Figure 1: Schematic of study design

Dotted lines and arrows represent the timing of dosing decision.

*Dose may be adjusted or confirmed based on safety/tolerability and PK data (applicable).

The multiple dose portion of the study (Part B) will evaluate the tolerability, safety, and PK of SKL24741 after 14 days of dosing in healthy male subjects. Doses, dosing regimen, and food status (fasting vs. fed) used in Part B will be determined based on the outcome of Part A. The selection of the first dose level of SKL24741 in Part B will be determined based on safety and PK information from Part A.

During Part A and Part B, a sentinel dosing strategy will be used (Section 7.2). Safety reviews will be performed prior to dose escalation from one cohort to another (dose level increase). Dose escalation criteria and dose stopping rules (Section 7.3) will be applicable at any time.

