Part B is a multiple-dose escalation study in 32 healthy male subjects. Doses, dosing regimen, and food status (fasting vs. fed) used in Part B will be determined based on the outcome of Part A. Dosing will extend over a 14-day period at each dose level. Four dose levels will be assessed, and subjects will be randomized into one of the four dose levels. Each dosing cohort will have 8 new subjects (6 subjects randomized to SKL24741 and 2 to placebo) dosed each day for 14 days ([Table 4](#)). Daily dose level in Part B will not exceed the maximum dose level used in Part A.

At each dose level, a sentinel dosing strategy will be used as described in Section [7.2](#).

Table 4: Study Design

Part A: Single Ascending Doses (SAD)			
Total Number of Subjects	Randomized Stratification (Active/Placebo)	Number of Subjects per Cohort	Food Status (Fasting/Fed)
60 Male Subjects	10 mg SKL24741/Placebo	4 SKL24741/ 2 Placebo	Fasting

	25 mg SKL24741/Placebo	4 SKL24741/ 2 Placebo	Fasting
	50 mg SKL24741/Placebo	4 SKL24741/ 2 Placebo	Fasting
	100 mg SKL24741/Placebo	4 SKL24741/ 2 Placebo	Fasting
	200 mg SKL24741/Placebo	4 SKL24741/ 2 Placebo	Fasting
	300 mg SKL24741/Placebo	4 SKL24741/ 2 Placebo	Fasting
	400 mg SKL24741/Placebo	4 SKL24741/ 2 Placebo	Fasting
	600 mg SKL24741/Placebo	4 SKL24741/ 2 Placebo	Fasting
	800 mg SKL24741/Placebo	4 SKL24741/ 2 Placebo	Fasting
	1000 mg SKL24741/Placebo	4 SKL24741/ 2 Placebo	Fasting

Part A: Food Effect Assessment

Total Number of Subjects	Dose	Number of Subjects per Cohort	Food Status (Fasting/Fed)
6 Male Subjects*	Based on the outcome of Part A	6 SKL24741	Fed

Part A: Gender Effect Assessment

Total Number of Subjects	Dose	Number of Subjects per Cohort	Food Status (Fasting/Fed)
6 Female Subjects (non-childbearing potential)	Based on the outcome of Part A	6 SKL24741	Fasting

Note:

- All doses are in a capsule formulation.
- Subjects will remain in the clinic for a 4-night stay (discharged on Study Day 4).
- A sentinel dosing strategy (Section 7.2) will be used for all cohorts, except for food and gender effect cohorts, in Part A.

* Refer to Section 7.1 regarding the subjects returning to the CRU for the food effect assessment.

Part B: Multiple Ascending Doses (MAD)

Total Number of Subjects	Randomized Stratification (Active/Placebo)	Number of Subjects per Cohort	Food Status (Fasting/Fed)
32 Male Subjects	SKL24741 Dose 1/Placebo	6 SKL24741/2 Placebo	Based on the outcome of Part A

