7.2. Dosing strategy

A sentinel dosing strategy will be used in both Part A (SAD) and Part B (MAD), except for the food and gender effect cohorts. The investigator and the Sponsor will assess safety and tolerability data and determine whether it is acceptable to continue dosing (within cohorts) or to dose escalate (between cohorts).

[Table 5](#) summarizes the sentinel dosing strategy as the following. The first 2 subjects (1 on SKL24741 and 1 on placebo) within each cohort may be dosed at the same time. Randomization will ensure that one of these 2 subjects (sentinel subjects) receives placebo. If the doses are safe and tolerated, as determined by the investigator and the Sponsor, dosing of the remaining subjects will occur after the observation period as specified in [Table 5](#).

Table 5: Sentinel Dosing Strategy

Dose level (Part A and Part B)	Observation Period and Safety Review
First dose level	1) Two sentinel subjects (1 on SKL24741 and 1 on placebo) 2) 14-day observation period after dosing the first subject with SKL24741 3) The investigator and the Sponsor review all available blinded safety data at the end of observation period. 4) The remaining subjects dosed within the cohort
Second dose level and higher	1) Two sentinel subjects (1 on SKL24741 and 1 on placebo) 2) 7-day observation period after dosing the first subject with SKL24741 3) The investigator and the Sponsor review all available blinded safety data at the end of observation period. 4) The remaining subjects dosed within the cohort

Dose escalation between the cohorts (dose increase) will only proceed if the safety and tolerability of the previous dose(s) are acceptable as judged by the investigator and the Sponsor. If available/needed, PK analysis results will also be considered. The investigator and the Sponsor may adjust the observation period based on the disposition of SKL24741.

The initiation and the final choice of the dose level for the food and gender effect cohorts (single dose administration) will not be performed until the PK and safety/tolerability are considered to be acceptable for the dose level provided under fasting condition and in healthy male subjects, respectively (Part A, single dose administration) ([Figure 1](#) and [Section 7.1](#)).

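### The rat NOAEL exposure limit in Section 4.2.2 is absolute, but the rule that enforces it (Table 6, Situation 3) acts only after the event and is loosely worded, and PK review is not a stated condition of each Part A escalation

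*Protocol*

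**What the plan says.** **The limit.** Protocol Section 4.2.2 gives two exposure levels. The dog NOAEL level (mean Cmax 2.61 µg/mL, AUC 21.7 µg*h/mL) is the aim of the Part A escalation, but it may be passed: "A few additional single dose levels beyond the dog NOAEL exposures may be considered". For those levels, "the dose escalation increment will not exceed 1.5-fold between each dose level". The rat NOAEL level (mean Cmax 3.32 µg/mL, AUC 61.2 µg*h/mL) is absolute: human exposure will in no case "exceed the exposure observed at the NOAEL of 15 mg/kg/day in rats". Section 4.1.1.3 labels both AUC values as 24-hour AUC. Section 4.2.2 also says that dose levels "will be adjusted if needed based on plasma exposure, safety and tolerability observed at each dose level".

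**The rules meant to keep to it.** Table 6 in Section 7.3 lists three situations in which the dose is not escalated. Situation 3 applies once plasma exposure has gone beyond the range of doses supported in Section 4.2.2. On what is reviewed between cohorts:

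- Section 4.2.1: "Safety reviews will be performed prior to dose escalation from one cohort to another".
- Section 7.2: "If available/needed, PK analysis results will also be considered".
- Section 7.3: blinded safety data are reviewed, with PK where applicable.
- Section 9.10.2: preliminary PK goes to the sponsor, blinded, after each cohort.

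**Where PK is an express condition.** Section 7.2 says that the start and final dose of the food and gender cohorts "will not be performed until the PK and safety/tolerability are considered to be acceptable for the dose level". Section 7.3 sets a like condition on the first Part B dose.

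**The concern.** A promise that exposure will never pass a given value can be kept only by looking ahead: the exposure expected at the next dose has to be judged from the PK already observed. Situation 3 looks back. A cohort just under the limit does not trigger it, and if the next cohort lands above the limit, the promise is already broken when the rule acts.

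The wording adds a second difficulty. Situation 3 sets an exposure against a range of doses and names neither Cmax nor AUC. The two parameters reach the rat level at very different points, so the choice can change the decision.

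This is a first-in-human study of a compound that the protocol describes as having a steep dose response. In the 28-day rat study (Section 4.1.1.3), transient ataxia and hypoactivity appeared at 30 mg/kg/day, twice the NOAEL dose. The rule belongs in the protocol: Section 11 requires the analysis plans only before database lock, so they need not exist when doses are being escalated.

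**Working it through.** **1. The plan's own figures.** Table 3 reproduces. Rat: 15/6.2 = 2.42 mg/kg, and 2.42/10 × 60 kg = 14.5 mg. Dog: 10/1.8 = 5.56 mg/kg, and 5.56/10 × 60 kg = 33.3 mg. There is no error in the starting dose.

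**2. Room between the two levels (Section 4.2.2).**

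- Cmax: 3.32/2.61 = 1.27.
- AUC: 61.2/21.7 = 2.82.

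Cmax is the tighter limit when exposure is at the dog level.

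**3. One step from the dog level.** Assumption: exposure is proportional to dose^b. No human data exist, and Section 4.1.1.2 reports that dose proportionality varied in animals, so b = 1 is shown with a range of 0.8 to 1.2. Next Cmax = 2.61 × (dose ratio)^b.

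| Dose ratio | b | Next Cmax (µg/mL) | Relative to 3.32 |
|---|---|---|---|
| 1.5 | 1.0 | 3.92 | 1.18 |
| 1.5 | 0.8 | 2.61 × 1.383 = 3.61 | 1.09 |
| 1.5 | 1.2 | 2.61 × 1.627 = 4.25 | 1.28 |
| 1.33 | 1.0 | 3.48 | 1.05 |
| 1.25 | 1.0 | 3.26 | 0.98 |

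AUC after a 1.5-fold step with b = 1 is 21.7 × 1.5 = 32.6, well under 61.2. A reading of Situation 3 on AUC alone would therefore not register the Cmax overshoot even afterwards.

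**4. Largest step from the dog level that stays within the limit.** 1.272^(1/b): 1.35 for b = 0.8, 1.27 for b = 1, 1.22 for b = 1.2. The 1.5-fold cap is wider than all three.

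**5. The listed ladder (Table 4).** From 200 mg upward the ratios are 300/200 = 1.5, 400/300 = 1.33, 600/400 = 1.5, 800/600 = 1.33 and 1000/800 = 1.25. If a cohort were at the dog Cmax, only the last of these would stay under the limit with b = 1.

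**6. Where a forward-looking rule would start to bind (b = 1).** Mean Cmax above 3.32/1.5 = 2.21 before a 1.5-fold step, 3.32/1.333 = 2.49 before a 1.33-fold step, and 3.32/1.25 = 2.66 before a 1.25-fold step.

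**The case against.** The strongest reply is that the protocol already contains the limit and several exposure-based controls:

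- Situation 3 cites Section 4.2.2 by number, and Situation 1 turns on AUC. Neither can be checked without PK, so Table 6 presupposes it.
- A note to Figure 1 lets PK inform dosing decisions. The figure itself is not shown, so its timing cannot be read.
- IRB notice is due before any added cohort beyond dog NOAEL exposure, which requires that cohort's exposure to be anticipated.
- Preliminary PK goes after each cohort to the sponsor, who shares the escalation decision. Doses may be adjusted on exposure.
- The 1.5-fold figure is a maximum, and a step expected to pass the rat level is already forbidden.

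All of this stands. A reader might infer that Section 7 leaves the limit without effect, or that no other safeguard anticipates exposure; the documents do not support either inference. A reader might also infer that it is open whether a single subject's value counts. Section 4.2.2 states its limits as mean values, so the cohort mean is the natural reading, and nothing here rests on the other.

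The reply does not supply a sentence that makes PK review a condition of each Part A escalation, or a rule that acts before the limit is passed. The protocol writes a PK condition for the food and gender cohorts and for the start of Part B, but words PK as optional between Part A cohorts.

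**Conclusion.** The point holds as a gap between an absolute limit and the rule that enforces it. Three features of the text carry it: Situation 3 is reactive, it names neither the parameter nor the limit values, and PK review is not a stated condition of each Part A escalation. None of these depends on a PK assumption.

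The size does depend on one. For a cohort at the dog NOAEL Cmax and a full 1.5-fold step, the next mean Cmax would be 18% over the rat limit under dose proportionality, and 9% to 28% over for an exponent of 0.8 to 1.2. This is an illustration, not a forecast. It supposes that a cohort lands at 2.61 µg/mL and that the team takes the full step without projecting exposure, although Section 4.2.2 forbids passing the limit. PK will probably be seen in practice. The point is worth correcting because an absolute safety limit should not rest on a step that the text leaves optional.

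**What to change.** Reword Table 6, Situation 3, along these lines:

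> Do not escalate to a dose at which the mean exposure of active subjects, projected from available PK, would exceed Cmax 3.32 µg/mL or AUC24hr 61.2 µg*h/mL, or if the observed cohort mean exceeds either. A smaller step that stays within both limits may be taken.

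In Sections 7.2 and 7.3, make review of the preceding cohort's preliminary PK a condition of each Part A escalation. The bioanalytical laboratory is already unblinded (Section 9.10.1) and can supply the active-subject mean without subject-level assignments, so the team stays blinded.

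**Cost.** Amendment wording only; the samples and the PK transfer after each cohort are already planned. Some escalations may wait for bioanalysis, and there may be smaller or fewer steps near the limit. Projection lowers the chance of passing the limit but cannot guarantee against it.

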5. STUDY OBJECTIVES

Part A

Primary:

- To evaluate the safety and tolerability of single oral ascending doses of SKL24741 capsule(s) administered to healthy male subjects

Secondary:

- To evaluate the PK of SKL24741 (R-enantiomer), SKL24742 (S-enantiomer) (if appropriate), and its possible metabolites (if deemed necessary) following administration of single oral ascending doses of SKL24741 capsule(s) administered to healthy male subjects
- To assess the food effect on the PK of SKL24741 and SKL24742 (if appropriate) following administration of a single oral dose of SKL24741 capsule(s) administered to healthy male subjects
- To assess the gender effect on the PK of SKL24741 and SKL24742 (if appropriate) following administration of a single oral dose of SKL24741 capsule(s) administered to healthy female subjects

Part B

Primary:

- To evaluate safety and tolerability of multiple oral ascending doses of SKL24741 capsule(s) administered for 14 days to healthy male subjects

Secondary:

- To evaluate the PK of SKL24741, SKL24742 (if appropriate), and its possible metabolites (if deemed necessary) following administration of multiple oral ascending doses of SKL24741 capsule(s) administered to healthy male subjects

6. STUDY ENDPOINTS

6.1. Primary Endpoint

Safety and tolerability will be based on assessment of adverse events, clinically significant laboratory assessments, electrocardiograms (ECGs), vital signs (blood pressure, heart rate, body temperature, respiratory rate, arterial oxygen saturation (SaO₂) (using pulse oximetry)), physical examinations, peak expiratory flow rate (PEFR), and Columbia-Suicide Severity Rating Scale (C-SSRS) (Part B only).

6.2. Secondary Endpoints

PK parameters will be calculated for SKL24741 and SKL24742 (if appropriate) from plasma and urine PK data.

7. STUDY DESIGN

7.1. Overview of Study Design

This is a two-part, double-blinded, randomized study of SKL24741. The schematic of study design is shown in [Figure 1](#). [Table 4](#) further outlines the study design.

Part A is a single-dose escalation study in healthy male subjects, except for the gender effect cohort in healthy female subjects. It is expected that a total of 66 subjects (60 male and 6 female subjects) will be enrolled in Part A. Each subject will be given a single oral dose of study drug capsule (SKL24741 or placebo) on one occasion. There will be 6 new subjects at each dose level (4 subjects randomized to SKL24741 and 2 to placebo) during single-dose escalation. Study drug will be administered under fasting condition, except for one cohort utilized for the food effect assessment at one of the dose levels.

To evaluate the magnitude of the food effect on the disposition of SKL24741, a cohort of subjects will receive a second dose of study drug under fed condition (Period 2) at an appropriate dose level based on PK results. After completing Period 1 (fasting) as part of single dose escalation, these subjects will return to the clinical research unit (CRU) for a second confinement to receive a second single dose (same dose level) of study drug under fed condition. A washout period of at least 14 days is planned between fasting and fed cohorts (i.e., between Period 1 and Period 2). As subjects complete the Follow-up visit of Period 1 and then return to the CRU for re-admission (Day -1 of Period 2), the same study procedures will apply again (including Day -1 procedures) in order to initiate Period 2.

To assess the gender effect on the disposition of SKL24741, a set of 6 female subjects of non-childbearing potential will be treated at one dose level under fasting condition.

At each dose level, except for the food and gender effect cohorts, a sentinel dosing strategy will be used as described in Section [7.2](#).

Part B is a multiple-dose escalation study in 32 healthy male subjects. Doses, dosing regimen, and food status (fasting vs. fed) used in Part B will be determined based on the outcome of Part A. Dosing will extend over a 14-day period at each dose level. Four dose levels will be assessed, and subjects will be randomized into one of the four dose levels. Each dosing cohort will have 8 new subjects (6 subjects randomized to SKL24741 and 2 to placebo) dosed each day for 14 days ([Table 4](#)). Daily dose level in Part B will not exceed the maximum dose level used in Part A.

At each dose level, a sentinel dosing strategy will be used as described in Section [7.2](#).

Table 4: Study Design

Part A: Single Ascending Doses (SAD)			
Total Number of Subjects	Randomized Stratification (Active/Placebo)	Number of Subjects per Cohort	Food Status (Fasting/Fed)
60 Male Subjects	10 mg SKL24741/Placebo	4 SKL24741/ 2 Placebo	Fasting

	25 mg SKL24741/Placebo	4 SKL24741/ 2 Placebo	Fasting
	50 mg SKL24741/Placebo	4 SKL24741/ 2 Placebo	Fasting
	100 mg SKL24741/Placebo	4 SKL24741/ 2 Placebo	Fasting
	200 mg SKL24741/Placebo	4 SKL24741/ 2 Placebo	Fasting
	300 mg SKL24741/Placebo	4 SKL24741/ 2 Placebo	Fasting
	400 mg SKL24741/Placebo	4 SKL24741/ 2 Placebo	Fasting
	600 mg SKL24741/Placebo	4 SKL24741/ 2 Placebo	Fasting
	800 mg SKL24741/Placebo	4 SKL24741/ 2 Placebo	Fasting
	1000 mg SKL24741/Placebo	4 SKL24741/ 2 Placebo	Fasting

Part A: Food Effect Assessment

Total Number of Subjects	Dose	Number of Subjects per Cohort	Food Status (Fasting/Fed)
6 Male Subjects*	Based on the outcome of Part A	6 SKL24741	Fed

Part A: Gender Effect Assessment

Total Number of Subjects	Dose	Number of Subjects per Cohort	Food Status (Fasting/Fed)
6 Female Subjects (non-childbearing potential)	Based on the outcome of Part A	6 SKL24741	Fasting

Note:

- All doses are in a capsule formulation.
- Subjects will remain in the clinic for a 4-night stay (discharged on Study Day 4).
- A sentinel dosing strategy (Section 7.2) will be used for all cohorts, except for food and gender effect cohorts, in Part A.

* Refer to Section 7.1 regarding the subjects returning to the CRU for the food effect assessment.

Part B: Multiple Ascending Doses (MAD)

Total Number of Subjects	Randomized Stratification (Active/Placebo)	Number of Subjects per Cohort	Food Status (Fasting/Fed)
32 Male Subjects	SKL24741 Dose 1/Placebo	6 SKL24741/2 Placebo	Based on the outcome of Part A
	SKL24741 Dose 2/Placebo	6 SKL24741/2 Placebo	Based on the outcome of Part A
	SKL24741 Dose 3/Placebo	6 SKL24741/2 Placebo	Based on the outcome of Part A
	SKL24741 Dose 4/Placebo	6 SKL24741/2 Placebo	Based on the outcome of Part A

Note:

- All doses are in a capsule formulation.
- Each cohort of 8 subjects will receive the study drug each day for 14 days. Subjects will remain in the clinic for a 17-night stay (discharged on Study Day 17).
- Doses, dosing regimen, and food status (fasting vs. fed) used in Part B will be determined based on the outcome of Part A.
- A sentinel dosing strategy (Section 7.2) will be used for all cohorts in Part B.

A cohort of female subjects will be added to **Part A** for the preliminary gender effect assessment as shown in [Table 4](#). These female subjects will need to be of non-childbearing potential, have undergone a sterilization procedure at least 6 months prior to dosing with official documentation (e.g., hysteroscopic sterilization, bilateral tubal ligation or bilateral salpingectomy, hysterectomy, or bilateral oophorectomy), or be postmenopausal with amenorrhea for at least 1 year prior to dosing and follicle-stimulating hormone (FSH) serum levels consistent with postmenopausal status as per Principal Investigator's judgment.

